# **1 INTRODUCTION**

#### 1.1 Background

With more than 2 million abdominal operations occurring annually in the United States (US), up to 20% of those patients developing ventral incisional hernias, abdominal wall defects and incisional hernias represent a challenging surgical condition. Approximately 250,000 ventral hernia repairs are performed on a yearly basis. There are several options for repair, including primary repair, synthetic or biologic material placement, repair with relaxing incisions, and use of musculofascial flaps, utilizing both open and laparoscopic approaches. However, there is no clear-cut consensus regarding the optimal hernia repair technique, particularly in complex hernia repair cases where patient co-morbidities exist and a high risk of infection is present.

Simple suture repair has been associated with a high risk of hernia recurrence, with reports ranging from 10% to 55%, and has been nearly abandoned for the repair of hernias which are greater than five centimeters (cm) in size. As a result, many ventral hernia repair procedures involve the use of a mesh material.

Synthetic mesh repair procedures, either open or laparoscopic, have been reported to lead to fewer recurrences compared to primary repairs. Improved outcomes are believed to be related to reduced tension on the fascial edges and sutures when mesh is used in hernia repair procedures. However, complex cases and large abdominal wall defects continue to pose a challenge to surgeons. Factors such as patient co-morbidities, defect size, location, tissue viability and degree of contamination are included in a surgeon's assessment and decision-making process. These large abdominal wall defects have been associated with recurrence rates of up to 46%.

Despite reducing hernia recurrence rates, the use of synthetic mesh has been associated with complications such as infection, adhesions, fistulae, and foreign body reactions including increased inflammation and/or connective tissue deposition.

Non-absorbable meshes can lead to complications related to the body's reaction to the persistent foreign mesh material resulting in foreign body sensations including discomfort and chronic pain, which is described by the International Association for the Study of Pain as pain lasting for 3 months or greater following hernia repair.

Ideally, an absorbable mesh would provide adequate structural support throughout the healing process and would be fully absorbed when the wound has completely healed, thereby potentially reducing the chances for complications associated with the persistence of non-absorbable mesh material. However, the development of absorbable mesh products has faced challenges related to the rate of absorption with complications arising when the mesh product is absorbed too quickly. Rapid absorption does not support sufficient healing if structural reinforcement is diminished during the tissue repair period. An absorbable mesh should

retain its functional strength for a sufficient period of time to allow native cellular ingrowth tissue remodeling, maturation of collagen, and gradual shift of mechanical load.

PhasixTM Mesh is a commercially available medical device in the US. It is a resorbable mesh prepared from poly-4-hydroxybutrate (P4HB) which has been studied for use as a biomaterial for a number of applications in medical devices and tissue engineering due to favorable mechanical properties, biocompatibility and desirable degradation times. Using standard measures of mechanical strength (suture pull-out, tear and ball burst strength) PhasixTM Mesh is comparable in performance to traditional polypropylene mesh. Pre-clinical implantation studies indicate that the resorption of the PhasixTM Mesh fibers is minimal throughout the 12 week expected period of healing and up to ~26 weeks post-implantation. Resorption of the fibers is essentially complete in 12-18 months. Given the long-term strength retention observed in preclinical studies, it is anticipated that PhasixTM Mesh may result in low recurrence and complication rates with minimal pain and discomfort when used for hernia repair.

A porcine bridging hernia repair study demonstrated that PhasixTM Mesh could perform as a durable scaffold for soft tissue repair when spanning a surgical defect. The results of the 52-week study showed that the repair site had significantly greater mechanical repair strength, as compared to native abdominal wall. This persisted even after significant PhasixTM Mesh resorption (as measured by molecular weight). PhasixTM Mesh showed an initial mild-moderate host inflammatory response, that declined to mild over 52 weeks. Neovascularization (angiogenesis) and new collagen deposition were evident at 6, 12, 26 and 52 weeks. In a 24-week rat study, histological analyses of the repair site demonstrated that some competitive meshes had a greater overall host inflammatory response, some had less of a response and one had a very similar response, to PhasixTM Mesh. In the same study, histological analyses demonstrated similar variability on measures of host fibrotic response.

MonoMax® suture (B. Braun Melsungen AG) is a product made from the same polymer as Phasix™ Mesh. A twelve month, 150-patient, multicenter clinical study demonstrated the safety and efficacy of MonoMax® for abdominal wall closure. Wound infection and wound dehiscence rates were compared between MonoMax® and an historical control (7.3% versus 11.3% combined). One year after surgery, the rate of incisional hernias was similar comparing the two groups: 21 patients (14.0%) in the MonoMax® group compared to 30 patients (21.3%) in the control.

This post-approval clinical study is being conducted to evaluate the use of PhasixTM Mesh in primary ventral, incisional or multiply-recurrent hernia repair in patients with a higher level of risk as defined by the presence of 1 or more common pre-existing conditions. Patients who receive a PhasixTM Mesh implant will be followed for 60 months.

# 1.2 Rationale

This study is intended to evaluate the use of Phasix™ Mesh for primary ventral, incisional and multiply-recurrent incisional hernia repair amongst subjects at high risk for complications. This protocol version (4.0) is intended to capture longer term data (through 60 months) on all eligible subjects. The protocol's follow up period was not extended due to safety related concerns or trends.

# **1.3 Device Descriptions**

# 1.3.1 Phasix™ Mesh

The PhasixTM Mesh (Davol, Inc.) is a resorbable mesh prepared from P4HB. P4HB is produced from a naturally occurring monomer and is processed into monofilament fibers and knitted into a surgical mesh. PhasixTM Mesh degrades through a process of hydrolysis and a hydrolytic enzymatic digestive process. It was developed to minimize the variability of resorption rate (loss of mass) and strength and provide support throughout the expected period of healing.

Pre-clinical implantation studies indicate that the resorption of the PhasixTM fibers is minimal throughout the 12-week expected period of healing and up to about 26 weeks post implantation. Resorption of the fibers is essentially complete in 12 to 18 months.

Phasix™ Mesh has been commercially available in the US since 2012 and is indicated to reinforce soft tissue where weakness exists, such as the repair of hernia or other fascial defects that require reinforcement or bridging material to obtain the desired surgical result. Because Phasix™ Mesh is fully resorbable, it should not be used in repairs where permanent wound or organ support from the mesh is required. A full description of Phasix™ Mesh is included in the product's Instructions for Use (IFU) (Appendix 2).

# **2** STUDY OBJECTIVES

The objective of this study is to collect additional data on safety, performance and effectiveness of Phasix™ Mesh in subjects requiring primary ventral, incisional or multiply-recurrent hernia repair in subjects at high risk for complications. Subjects at high risk are defined as having 1 or more of the following co-morbidity conditions: body mass index (BMI) between 30-40 kg/m^2, inclusive, active smokers, chronic obstructive pulmonary disease (COPD), diabetes, immunosuppression, coronary artery disease, chronic corticosteroid use, low pre-operative serum albumin, advanced age, or renal insufficiency. The study end points are described below.

# **3 STUDY ENDPOINTS**

There are two primary endpoints, hernia recurrence rate and surgical site infection (SSI) rate, and six secondary endpoints:

3.1 Primary Endpoints:

1. Hernia Recurrence Rate

Hernia recurrence rates will be assessed by physical examination at each study visit through 60 months. A recurrent hernia will be defined as any hernia identified or confirmed by the investigator, during any study follow-up visit, in approximately the same position as the hernia repaired in the study procedure. Potential hernias identified via incidental magnetic resonance imaging (MRI) or computed tomography (CT) scan will be evaluated by the operating surgeon for clinical significance and confirmation of hernia recurrence.

2. Surgical Site Infections

Infections at the surgical site will be assessed by physical examination at each study visit through 60 months. If an infection is suspected, a routine culture, obtained via each site's standard protocol, should be obtained to determine cell count and type (i.e. yeast, gram positive or gram negative bacteria, or other). If genus and species of the culture are identified as part of the routine practice at the site, that information should be recorded. Classification will follow the CDC guidelines for superficial and deep surgical site infections (Appendix 3).

- 3.2 Secondary Endpoints:
  - 1. Pain Visual Analog Scale (VAS)
  - 2. Device related adverse event incidence
  - 3. Rate of reoperation due to the index hernia repair
  - 4. Quality of life assessments (Carolinas Comfort Scale® and SF-12® 12-item short form health survey)
  - 5. Surgical procedure time as measured from incision to closure (skin to skin)
  - 6. Length of stay

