#### 6.3.3 Assessments

Subjects should report to their respective study site for follow-up visits at the following times:

- 1 month assessment: Day  $30 \pm 7$  days post device placement
- 3 month assessment: Day  $90 \pm 30$  days post device placement
- 6 month assessment: Day  $180 \pm 30$  days post device placement
- 12 month assessment: Day  $365 \pm 30$  days post device placement
- 18 month assessment: Day  $545 \pm 30$  days post device placement
- 24 month assessment: Day  $730 \pm 30$  days post device placement
- 30 month assessment: Day  $910 \pm 30$  days post device placement
- 36 month assessment: Day 1095 + 30 days post device placement
- 42 month assessment: Day 1275 + 30 days post device placement
- 48 month assessment: Day 1460 + 30 days post device placement
- 54 month assessment: Day 1640 + 30 days post device placement
- 60 month assessment: Day  $1825 \pm 30$  days post device placement

At each study visit (see exception below for the 30, 42, and 54 month assessments) the following procedures will be completed and these data recorded in source documentation and on the eCRF:

- Physical exam to check for hernia recurrence and surgical complications. Note: If the subject undergoes imaging for any reason and a recurrent hernia is identified, it must be recorded.
- Surgical Pain Scale (VAS)
- Carolinas Comfort Scale®
- SF-12®
- Concomitant pain medication usage (all pain medication will be captured at baseline. Hernia associated pain medication only will be captured at 12,24, 36, 48, and 60 months)
- Assessment of AEs/complications

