# 6.3.3.1 Roll in Visit

The Roll in Visit should be completed in clinic where eligible subjects should be reconsented and confirmed that no abdominal surgeries were performed at the site of the index procedure. Sites with IRB approval of the extension study may complete the Roll in Visit with eligible subjects in combination with the 36 Month Follow Up visit.

6.3.3.2 30 Month Follow Up (910 days  $\pm$  30 days), 42 Month Follow Up (1275  $\pm$  30 days), 54 Month Follow Up (1640 days  $\pm$  30 days)

A telephone contact should be scheduled with the subject and completed by the Investigator. The following information will be collected:

- Symptoms suggestive of hernia recurrence
- Symptoms suggestive of surgical site infections
- Any adverse events relating to the device, procedure, or abdominal space since the last study assessment

If the Investigator determines the responses provided by the subject demands a physical exam be conducted, an office visit will be scheduled. The office visit will be included as part of the 30, 42 or 54 Month Follow Up assessment (not an Unscheduled Visit) and will require all study assessments listed in Section 6.3.3 to be completed.

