## 1 General

This Statistical Analysis Plan (SAP) was defined by the Sponsor and the responsible Statistician. It is based upon the Study Protocol (version 4.0 of October 30, 2017) and contains detailed description of the statistical methods described therein.

The SAP describes prospectively the analyses to be performed on study data. It was finalized prior to data base lock.

This is a post-market, prospective, multi-center, open-label study designed to collect additional data on safety, performance and effectiveness of Phasix™ Mesh for primary ventral or incisional or multiply-recurrent hernia repair in subjects with a higher level of risk. Subjects at high risk are defined as having one or more of the following co-morbidity conditions: body mass index (BMI) between 30-40 kg/m^2, active smokers, chronic obstructive pulmonary disease (COPD), diabetes mellitus, immunosuppression, coronary artery disease, chronic corticosteroid use, serum albumin less than 3.4 g/dL, advanced age or renal insufficiency. Subjects who receive a Phasix™ Mesh implant will be followed for 60 months with follow-up visits conducted at 1, 3, 6, 12, 18, 24, 30, 36, 42, 48, 54 and 60 months following surgery. At the 30, 42 and 54 month visit a telephone contact should be scheduled with the subject. If the investigator determines the responses provided by the subject demands a physical examination be conducted, a clinic visit will be scheduled.

This clinical study is projected to enroll up to 120 subjects at approximately 16 US sites. The sample size of 120 subjects is based on potential adequacy of data to meet the study objectives. No formal sample size calculation was performed.

The two primary endpoints are hernia recurrence rate and surgical site infection (SSI) rate. There is no formal statistical hypothesis for this post-market study with a single treatment condition.

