##### 4.4.1 Analysis of Primary Variables

###### Hernia recurrence rate

Hernia recurrence rates will be assessed by physical examination at each study visit through 60 months. A recurrent hernia will be defined as any hernia identified or confirmed by the investigator, during any study follow-up visit, in approximately the same position as the hernia repaired in the study procedure. Potential hernias identified via incidental magnetic resonance imaging (MRI) or computed tomography (CT) scan will be evaluated by the operating surgeon for clinical significance and confirmation of hernia recurrence.

Hernia recurrence (after surgery including UVs) is defined as follows:

- The question “Is there any evidence of hernia recurrence in the same location as the index procedure per physical exam?” is answered with “yes”

or

- the question “Is there any evidence of hernia recurrence in the same location as the index procedure by any other means?” is answered with “yes”.

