If a hernia recurrence occurs, a corresponding adverse event has to be documented. The start date of the corresponding AE is used to determine the time point of hernia recurrence. The rate of hernia recurrence will be classified in time intervals (as defined in section 4 above): post OP – 1 month, > 1 month – 3 months, > 3 months – 6 months, > 6 months – 12 months, > 12 months – 18 months, > 18 months – 24 months, > 24 months – 30 months, > 30 months – 36 months, > 36 months – 42 months, > 42 months – 48 months, > 48 months – 54 months, > 54 months – 60 months. The time of a hernia recurrence is calculated as start date of the corresponding AE minus date of device placement (surgery at Day 0). In case of more than one hernia recurrence per subject in an interval, the recurrences are counted only once per interval. In case a scheduled visit was not performed but the subject had a visit afterwards, the total number of subjects will not be reduced for the concerned time interval as the subject is still in study. If no information is available that a hernia recurrence occurred until the missed visit, no hernia recurrence is assumed for that time interval. The total number of subjects per time interval will be reduced by the number of subjects discontinued in a time interval if the time interval was not completed (according to the predetermined time windows). However, if a hernia recurrence occurred in a not completed interval the subject is counted for that interval. The date of completion or discontinuation from the end of study

page or the last visit date if the subject was lost to follow up will be used to determine the study duration of each subject since surgery at Day 0. In addition to the recurrence rates per time interval, the overall hernia recurrence rate will be calculated considering the time from post OP to end of study irrespective of the individual study duration. In case of more than one hernia recurrence per subject, the recurrences are counted only once.

Exact two-sided 95% confidence intervals (CIs) for hernia recurrence = “yes” using the SAS procedure PROC FREQ with option BINOMIAL will be calculated per time interval and overall.

The hernia recurrence rates by time intervals (visit) and overall will additionally be presented by the subgroups described in section 3.4 above (for subgroup ‘gender’ with 95%-CIs and for subgroups ‘center’, ‘pre-operative diagnosis’ and ‘surgical procedure’ without 95%-CIs).

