#### Pain medication

All current pain medication is captured at baseline. Hernia associated pain medication is captured at 12, 24, 36, 48 and 60 months. All documented pain medication will be coded by world health organization drug dictionary (WHO-DD) and will be tabulated by anatomical therapeutic chemical classification (ATC) level 1, level 4 and WHO-DD preferred term.

A frequency table by Month 1, Month 3, Month 6, Month 18, Month 30, Month 42 and Month 54 visit (Month 30, 42 and 54 only if clinic visits were performed) will be presented showing the intake of prescription or OTC medications for treatment of pain related to hernia repair (yes/no) including the classification in “non-narcotic” and “narcotic” if “yes”.

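### The endpoint text promises an examination at every visit, but months 30, 42 and 54 are telephone contacts with their own recurrence rates; adding 12-month rows that end at an examination is a cheap improvement.

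*Protocol*

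**What the plan says.** - **Endpoint text.** Protocol 3.1 and SAP 4.4.1 use the same sentence for recurrence: "Hernia recurrence rates will be assessed by physical examination at each study visit through 60 months". Both make a parallel statement for SSI.
- **Schedule.** Protocol 6.3.3 carves out an exception: "At each study visit (see exception below for the 30, 42, and 54 month assessments) the following procedures will be completed". For those three time points Protocol 6.3.3.2 says: "A telephone contact should be scheduled with the subject and completed by the Investigator". The call covers symptoms of recurrence, symptoms of infection, and adverse events. An office visit follows only if the investigator judges that the answers demand an examination. SAP section 1 agrees: "At the 30, 42 and 54 month visit a telephone contact should be scheduled with the subject". The Table of Study Events (Protocol 6.4) has no examination mark at 30, 42 or 54 months.
- **Analysis.** SAP section 4 defines intervals that include Days 761-940, 1126-1305 and 1491-1670. SAP 4.4.1 gives each its own recurrence rate with an exact 95% confidence interval.
- **Event date.** "The start date of the corresponding AE is used to determine the time point of hernia recurrence".
- **Denominator.** "The total number of subjects per time interval will be reduced by the number of subjects discontinued in a time interval" if the interval was not completed; a subject with a recurrence in it is still counted.
- **Other routes to detection.** A recurrence also counts if this question is answered yes: "Is there any evidence of hernia recurrence in the same location as the index procedure by any other means". Unscheduled visits feed the primary endpoints (SAP section 4).

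**The concern.** The endpoint sentence carries no exception for the three telephone contacts, so in both documents it disagrees with the schedule. The consequence lies in the 6-month table. After month 24, intervals that end with a call alternate with intervals that end with an examination. A subject who had only the call stays in the denominator and is event-free for that interval unless an event is later dated into it. A recurrence without symptoms is first seen at the next examination. If its adverse event (AE) start date is then the detection date, it moves into the following interval.

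The resulting low-high pattern could be read as a change in risk when it reflects when subjects were examined. Long-term recurrence is what the extension was added to describe (Protocol 1.2 and 7.1), so the late rows will be read with interest.

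**Working it through.** **1. Which intervals contain a scheduled examination?** From the windows in SAP section 4 (visit day ± 30):

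| Visit | Window (days) | Contact | SAP interval (days) |
|---|---|---|---|
| 24 | 700-760 | clinic | 576-760 |
| 30 | 880-940 | telephone | 761-940 |
| 36 | 1065-1125 | clinic | 941-1125 |
| 42 | 1245-1305 | telephone | 1126-1305 |
| 48 | 1430-1490 | clinic | 1306-1490 |
| 54 | 1610-1670 | telephone | 1491-1670 |
| 60 | 1795-1855 | clinic | 1671-end of study |

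With visits in window, the three telephone intervals contain no scheduled examination. The one exception is a Roll-in visit held separately from month 36: it includes an examination and has no day window. Each interval limit is the upper end of a visit window, so the 6-month pairs join without gap or overlap: 761-1125 (365 days), 1126-1490 (365 days) and 1491-end of study.

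**2. How large could the shift be?** The plan states no recurrence rate to reproduce. All inputs below except the day limits are assumptions:
- constant hazard, with 60-month risk R = 20% (range 10-30%);
- s = share of recurrences arising in the telephone interval that are found in it;
- b = share of the rest whose start date is back-dated to true onset.

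Hazard: λ = -ln(1-R)/1825 = 0.22314/1825 = 0.00012227 per day; S(t) = exp(-λt).

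S(760) = 0.91126, S(940) = 0.89142, S(1125) = 0.87149. The true rates are therefore
- >24-30 months: inc1 = 1.984%;
- >30-36 months: inc2 = 1.994%.

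Reported rates:
- telephone interval = inc1 × [s + (1-s)b];
- next interval = inc2 + inc1 × (1-s)(1-b).

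At s = 50%:

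| b | >24-30 | >30-36 | Ratio |
|---|---|---|---|
| 0% | 1.984 × 0.50 = 0.992% | 1.994 + 0.992 = 2.986% | 3.0 |
| 50% | 1.984 × 0.75 = 1.488% | 1.994 + 0.496 = 2.490% | 1.7 |
| 100% | 1.984% | 1.994% | 1.0 |

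Over s = 25-75% and b = 0-100% the ratio runs from 1.0 to 7.0; 7.0 is the extreme corner (s = 25%, b = 0). At s = 50%, b = 0 it is 3.03 for R = 10% and 2.98 for R = 30%. The two rows always sum to inc1 + inc2, because the shift stays inside the 12-month interval.

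**3. Would it be visible?** Expected events at R = 20%, s = 50%, b = 0:
- 120 at risk: 120 × 0.992% = 1.2 against 120 × 2.986% = 3.6;
- 60 at risk: 0.6 against 1.8.

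Exact 95% intervals overlap: 1/120 gives 0.0-4.6% and 4/120 gives 0.9-8.3%; 1/60 gives 0.0-8.9% and 2/60 gives 0.4-11.5%. The figure of 120 is an enrolment ceiling that includes screen failures, and the extension needs re-consent and site approval, so fewer will be at risk late on.

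**4. What do 12-month rows do under the SAP denominator rule?** Event-free subjects who leave during an interval are removed, while cases stay. Take 100 starters and 4 recurrences in the year (4.0% of starters), with an assumed share of remaining subjects leaving event-free per half-year:
- 5%: denominator 100 × 0.95² = 90.25; 4/90.25 = 4.4%;
- 10%: denominator 100 × 0.90² = 81; 4/81 = 4.9%.

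The longer row removes the examination-timing shift but enlarges this dropout effect.

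**The case against.** **The schedule is disclosed.** Protocol 4 points to Section 6 for detail, Protocol 6.3.3 states the exception, and SAP section 1 repeats it. Nobody would be misled about conduct. This stands: the text defect is one unqualified sentence per endpoint, repeated in both documents.

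**Allocation is by AE start date, not by visit.** A recurrence found at month 36 with onset on Day 900 counts in >24-30 months. The shift therefore needs start dates set at detection. The documents do not say how the date is set, and a rule may sit in eCRF instructions outside these documents. This also stands and is why the effect is stated conditionally. Symptom-prompted office visits, unscheduled visits, incidental imaging and the second recurrence question limit it further.

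**Kaplan-Meier and an overall rate are already planned**, and ad hoc analyses are allowed. True, but no reading times are fixed for the curve, and the 6-month rows would otherwise carry the late-recurrence message.

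**Stronger readings that the documents do not support:**
- A reader might take the SAP's pain-medication table, which uses "Month 30, 42 and 54 only if clinic visits were performed", as proof that the same condition was overlooked for recurrence. It is not. The call does not collect pain medication, so that table must be confined to clinic visits, whereas the call does ask about recurrence symptoms and adverse events.
- A reader might infer that the primary result is biased. A shift between adjacent intervals leaves the overall rate alone and largely spares Kaplan-Meier at 36, 48 and 60 months. Only readings at 30, 42 or 54 months share the problem.
- A reader who extends the constant-hazard illustration to all three 12-month rows gets 3.98%, 3.80% and 3.34%. These are not expected rates. The decline comes from keeping earlier cases in the denominator and from stopping at Day 1825, whereas the SAP's last interval runs to end of study.

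**Conclusion.** The point holds as a cheap improvement. The endpoint wording contradicts the schedule, and three 6-month recurrence rates describe periods with no scheduled examination apart from a possible separate Roll-in. To the extent that silent recurrences are dated when found, those rates are too low and the next ones too high. The illustrated ratio runs from 1.0 (full back-dating) to 7.0, and is 3.0 at s = 50% with no back-dating. It rests wholly on the assumed hazard, detection share and dating practice.

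The study is descriptive with no hypothesis, events per interval will be few, and confidence intervals will overlap. The gain is in how late recurrence is read.

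One related inconsistency matters for the remedy. In the Table of Study Events, footnote 3 (clinic visit at the investigator's discretion) is attached to the 60-month column. That conflicts with Protocol 6.3.3 and 6.3.3.2 and with the examination mark in the same column. The last 12-month row relies on that examination.

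**What to change.** 1. In SAP 4.4.1, add recurrence rates with exact 95% confidence intervals for Days 761-1125, 1126-1490 and 1491-end of study. Count each subject at most once per 12-month interval, with that interval's own denominator under the existing discontinuation rule. Do not add two 6-month percentages.
2. Base statements about late recurrence on these rows together with Kaplan-Meier estimates at 24, 36, 48 and 60 months.
3. Keep the 6-month rows, so that the table stays aligned with the SSI, reoperation and AE tables. Footnote that >24-30, >36-42 and >48-54 months contain telephone contacts and no scheduled examination other than a separate Roll-in.
4. In Protocol 3.1 and SAP 4.4.1, for both recurrence and SSI, replace the reference to every study visit with in-clinic visits, and describe 30, 42 and 54 months as telephone symptom contacts.
5. Reconcile footnote 3 on the 60-month column with Protocol 6.3.3, 6.3.3.2 and the examination mark in that column.

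**Cost.** Three table rows, four Kaplan-Meier readings, one footnote and wording edits; no new data. The price is less emphasis on 6-month detail after month 24 and more dropout inflation in the longer rows, which is why they belong beside Kaplan-Meier. The rows do not correct for examinations held after their window, or for subjects with a silent recurrence who leave before the next examination.
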